#### **2.4.2 For each patient, listings of each dose of the study drug administered along with dose change reasons will be produced. Prior, concomitant and post therapies**

Prior and concomitant therapies are defined as any medication, and significant non-drug therapies administered to a subject preceding or coinciding with the study assessment period.

Medications will be coded using the World Health Organization (WHO) Drug Reference Listing (WHO DRL) dictionary that employs the WHO Anatomical Therapeutic Chemical (WHO ATC) classification system.

Concomitant therapies will include medications and significant non-drug therapies taken between the first day of study medication and up to 30 days after the last day of study medication (see [Section 2.1.6](#) for the on-treatment period definitions).

Concomitant therapies will be summarized by ATC class, preferred term and treatment arm for the Safety Set 4. Medications starting prior to the start of study treatment and continuing after the start of study treatment will be included in this summary for the entire granule period as defined in [Table 2-1](#).

Prior therapies will include medications or significant non-drug therapies starting and ending prior to the start of study treatment. Prior therapies were summarized in the primary CSR analysis and will not be repeated for the final CSR.

All concomitant therapies will be listed for Safety Set 4.

#### **2.5 Analysis supporting primary objective(s)**

The primary objectives of this study are to evaluate patient compliance with study treatment, as measured by the count of deferasirox granule stick packs/dispersible tablets and to evaluate the

change in serum ferritin after 24 weeks of treatment for both formulations of deferasirox in pediatric ICT naive patients with iron overload during core phase. Cumulative data up to week 24 from all ICT naive patients was analyzed in the primary CSR as well as EoC CSR (reported descriptively) and will not be repeated for final CSR.

## **2.6 Analysis supporting secondary objectives**

Secondary variables include compliance after 48 weeks of treatment, changes in SF from baseline after 24 weeks in ICT pre-treated patients and after 48 weeks of treatment in ICT-naive and pre-treated patients, patient reported outcomes/observer reported outcomes and safety assessments (i.e. adverse events, laboratory parameters, vital signs, etc.). All secondary variables were analyzed in the EoC CSR and will not be repeated for the final CSR.

## **2.7 Safety analyses**

All analyses will be performed on the Safety Set-4 for the entire granule period. Listings will be provided for the Safety Set-4.

Unless otherwise specified, the safety summary tables will include only assessments from the on-treatment period. For the definition of on-treatment period, please see [section 2.1.6](#).

All data, regardless of observation period, will be listed. Safety assessments starting during the pre-treatment or post-treatment period will be flagged in the listings. Safety assessments starting prior to study day 1 will appear with negative study day in the listings.

Any COVID-19 related safety events will be flagged in listings.

### **2.7.1 Adverse events (AEs)**

AEs will be coded using the latest version of Medical Dictionary for Regulatory Activities (MedDRA) available prior to clinical database lock.

All aEs will be listed. Any information collected (e.g. regardless to study drug, action taken etc.) will be listed as well as the duration of the AE. The listings of all, serious adverse events, adverse events leading to study drug discontinuation, and adverse events requiring dose adjustment or interruption will also be provided.

The following adverse event summaries will be produced by treatment arm:

- Adverse events (overall and severe), regardless of study drug relationship by primary system organ class and preferred term
- Adverse events (overall and severe), with suspected study drug relationship by primary system organ class and by preferred term
- Serious adverse events (overall and severe), regardless of study drug relationship, by primary system organ class and preferred term
- Serious adverse events (overall and severe), with suspected study drug relationship, by primary system organ class and preferred term
- Adverse events leading to study drug discontinuation (overall and severe), regardless of study drug relationship, by primary system organ class and preferred term

- Adverse events requiring dose adjustment or study-drug interruption (overall and severe), regardless of study drug relationship, by primary system organ class and preferred term
- Adverse events requiring additional therapy (overall and severe), regardless of study drug relationship, by primary system organ class and preferred term
- An overall summary of type of AEs (e.g. serious, leading to study drug discontinuation, requiring dose adjustment or/and interruption) will be presented overall and by severe AEs and treatment arm.

### **Adverse events of special interest / grouping of AEs**

All AESI groupings are defined through the use of Preferred Terms (PT), High Level Terms (HLT), System Organ Classes (SOC), Standardized MedDRA Queries (SMQ), Novartis MedDRA Queries (NMQ) or through a combination of these components. All AESI definitions or AE groupings are specified in the electronic Case Retrieval Strategy (eCRS). The latest version of the eCRS available at the time of the analysis will be used.

AESI will be summarized by grouping, preferred term and treatment arm (specifying severity, SAE, relationship, leading to treatment discontinuation, leading to dose adjustment/interruption and requiring additional therapy).

A listing of all grouping levels down to the MedDRA preferred terms used to define each AESI will be generated.

#### **2.7.2 Deaths**

Deaths occurring on-treatment (i.e. within 30 days after discontinuation of study drug) as well as all deaths will be summarized by primary system organ class and preferred term. All deaths will be listed using safety set 3.

#### **2.7.3 Disclosure related analysis**

In order to provide a cumulative summary of AEs by treatment arm and by phase (core, extension) during the study for disclosure, the following arms need to be generated within a single XML file based on safety set 3.

- Deferasirox DT: CORE
- Deferasirox granules: CORE
- Deferasirox granules: Extension (including patients who already received granules in the core phase)
- Crossover to Deferasirox granules: Extension (including patients who received DT in core phase but crossed over to deferasirox granules during the extension phase)

For the legal requirements of ClinicalTrials.gov and EudraCT, two required tables on on-treatment adverse events which are not serious adverse events with an incidence greater than 5% and on on-treatment serious adverse events and SAE suspected to be related to study treatment will be provided by system organ class and preferred term on the safety set population.

If for a same patient, several consecutive AEs (irrespective of study treatment causality, seriousness and severity) occurred with the same SOC and PT:

- a single occurrence will be counted if there is  $\leq 1$  day gap between the end date of the preceding AE and the start date of the consecutive AE
- more than one occurrence will be counted if there is  $> 1$  day gap between the end date of the preceding AE and the start date of the consecutive AE

For occurrence, the presence of at least one SAE / SAE suspected to be related to study treatment / non SAE has to be checked in a block e.g., among AE's in a  $\leq 1$  day gap block, if at least one SAE is occurring, then one occurrence is calculated for that SAE.

The number of deaths resulting from SAEs suspected to be related to study treatment and SAEs irrespective of study treatment relationship will be provided by SOC and PT.

## 2.7.4 Laboratory data

### 2.7.4.1 Serum ferritin

Relative and absolute change from baseline in serum ferritin at every year visit during the extension period will be described for the Safety Set 4. A graphical presentation of mean and standard deviation of absolute value in serum ferritin during the study will be plotted by treatment arm and timepoint for safety set 4.

### 2.7.4.2 Other laboratory data

Laboratory data from all sources (central and local laboratories) will be combined. All laboratory values will be converted into International System (SI) units.

Raw values as well as absolute and relative change from baseline values for hematology, biochemistry and urinalysis laboratory parameters will be summarized descriptively per time window and treatment arm on the Safety Set 4 (see [Table 5-4](#) for time windows definition).

Shift tables based on normal ranges to compare baseline to the worst post-baseline value will be provided by parameter and treatment arm for hematology, biochemistry and urinary laboratory data. Same shift table will be provided based on notable/extended ranges for key safety laboratory parameters defined in [Table 2-4](#).

For notable/extended ranges below for each laboratory parameter, all patients satisfying the condition will be considered. For the other post-baseline categories, a patient will be counted only in the worst category (ie., categories are mutually exclusive).

**Table 2-4      Definition of notable/extended ranges for key safety laboratory parameters**

Laboratory parameters	Criteria for notable/extended ranges
Platelet count	$< 100 \times 10^9/L$ (extended range $< 50 \times 10^9/L$ )
Absolute neutrophils	$< 1.5 \times 10^9/L$ (extended range $< 0.5 \times 10^9/L$ )
Serum creatinine	$> 33\%$ increase from baseline and $> ULN$ at two consecutive measurements at least 7 days apart

Laboratory parameters	Criteria for notable/extended ranges
Recalculated creatinine clearance	<60 mL/min at two consecutive measurements at least 7 days apart (extended range <40 mL/min at two consecutive measurements at least 7 days apart)
Urinary protein/urinary creatinine ratio	> 1.0 (mg/mg) at two consecutive measurements at least 7 days apart
ALT/AST	>5 x ULN and >2 x baseline (extended range >10×ULN and >2×baseline value)

Recalculated creatinine clearance will be calculated using the Schwartz formula (for pediatric population at baseline) described in [Section 5.2.1](#). The Modification of Diet in Renal Disease (MDRD) derivation will be provided in the derived datasets only for possible future requests.

A listing of all laboratory values with values flagged to show the corresponding range classifications relative to the laboratory reference ranges will be provided by laboratory data and treatment arm based on Safety set 4. Assessment day relative to first dose of study drug will be included and all laboratory assessments collected outside of the on-treatment period will be flagged.

A listing of patients with laboratory abnormalities based on normal ranges and notable/extended ranges will also be provided for Safety set 4.

Normal ranges by laboratory parameter will also be provided in a separate listing.

### **Liver Function Parameters**

Liver function parameters of interest are total bilirubin (TBL), Alanine aminotransferase (ALT), Aspartate aminotransferase (AST) and alkaline phosphatase (ALP). The number (%) of subjects with worst post-baseline values as per Novartis Liver Toxicity guidelines will be summarized.

The following summaries will be produced:

- ALT > 3xULN
- ALT > 5xULN
- ALT > 8xULN
- ALT > 10xULN
- ALT > 20xULN
- AST > 3xULN
- AST > 5xULN
- AST > 8xULN
- AST > 10xULN
- AST > 20xULN
- ALT or AST > 3xULN
- ALT or AST > 5xULN
- ALT or AST > 8xULN
- ALT or AST > 10xULN
- ALT or AST > 20xULN
- TBL > 2xULN

- TBL > 3xULN
- ALT or AST > 3xULN & TBL > 2xULN
- ALT or AST > 3xULN & TBL > 2xULN & ALP >= 2xULN
- ALT or AST > 3xULN & TBL > 2xULN & ALP < 2xULN

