## Amendment 4 (15-Jun-2017)

### Amendment rationale

As of 15-Jun-2017, 178 patients have been randomized (60 chelation naïve and 118 pre-treated patients). The pre-treatment arm is fully accrued.

The purpose of this amendment is to include an interim analysis, allow for paper PRO completion, and clarify various points to improve site understanding and consistency in implementation of the protocol.

Amendment rationales are as follows:

1. With this amendment, one interim analysis has been added to allow for early analysis of the data if requested by the health authority.
2. To allow for paper PRO questionnaires use in case of technical issue or malfunctioning of the electronic device.
3. To clarify the completion of the ObsPRO questionnaires for patients who turn 10 years will continue to be completed by the caregiver.
4. To clarify the inclusion/exclusion criteria for the optional extension phase.
5. To clarify that when either TBIL or direct bilirubin are increased and  $> 2 \times$  ULN, it always needs to be checked whether there is also an increase of ALT/AST that meets the definition of DILI.
6. To modify the dose modification and exclusion criteria for direct bilirubin to enhance enrolment and reduce the amount of study drug interruptions without compromising safety. Many transfusion-dependent anemia patients have higher baseline level of direct bilirubin due to hemolysis. Implementation of these less strict exclusion and dose modification criteria will not have any impact on capturing patients with Drug induced liver injury as this only occurs in case of increase of direct bilirubin  $> 2 \times$  ULN.
7. To include dose modifications in case of Toxic epidermal necrosis (TEN) on Table 6-2 as per latest IB update.
8. To correct height and weight to monthly in the optional extension phase to align with the CRF and collection requirements.
9. To re-define Safety Set 4. At the end of the study, safety data for the optional extension phase data will be analyzed considering core and extension phases for patients who received granule formulation. The Safety Set 4 will be used and the FAS-4 has been removed.
10. Baseline categories for serum creatinine, creatinine clearance, ALT, AST and urine protein/creatinine ratio have been re-defined to align with the protocol exclusion and dose modification criteria.

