For patients with normal baseline ALT or AST or total bilirubin value:  AST or ALT >3.0xULN combined with total bilirubin >2.0xULN without evidence of cholestasis c OR (Note to study team: If supported by available data) For patients with elevated baseline AST or ALT or total bilirubin value  [AST or ALT>2x baseline AND >3.0xULN] OR [AST or ALT>8.0 ULN], whichever is lower, combined with total bilirubin >2x baseline AND >2.0xULN	Permanently discontinue patient from study drug treatment.  Repeat as soon as possible, preferably within 48 hours from awareness of the abnormal results, then with weekly monitoring of LFTs a , or more frequently if clinically indicated until AST, ALT, or bilirubin have resolved to baseline or stabilization over 4 weeks. Refer to Section 6.3.2 for additional follow-up evaluations as applicable.
Hepatic impairment	
Moderate hepatic impairment (Child-Pugh Class B)	The study medication will be interrupted and patient monitored. If liver disease prognosis improves, deferasirox can be reintroduced at 10 mg/kg/day for DT and at 7 mg/kg/day for granules or 50% of previous dose, whichever is less. While monitoring continues, dose may be increased by 5 mg/kg/day for DT and by 3.5 mg/kg/day for granules every 2 weeks, to a maximum of 50% of patient's previous dose if the investigator determines that dose increase is in the best interest of the patient. Study medication must be used with caution in such patients.
In patients who develop severe hepatic impairment (Child-Pugh Class C) during the study	Study medication must be discontinued.
Other dose modifications	
Changes in Serum Ferritin	

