Gastrointestinal issues (including diarrhea, constipation, nausea, vomiting and abdominal pain)	
Some basic recommendations, based on practical experience, can be made to guide physicians in managing patients who experience diarrhea.
 
At the first sign of diarrhea, consider anti-diarrheal medication such as loperamide. Remind the patient to discontinue any laxative preparations or stool softeners they may be taking and to eat small, frequent meals. Determine if the patient is lactose intolerant. Deferasirox DT contains lactose in the formulation so supplemental lactase may benefit the patient; however the deferasirox granules do not contain lactose. Remind the patient to drink 8 to 10 glasses of clear liquid per day. Suggest that the patient take their deferasirox DT with water, not with orange juice or apple juice until the diarrhea resolves.
 
Should the gastrointestinal issues (including diarrhea, constipation, nausea, vomiting and abdominal pain) persist, study drug may be discontinued if the investigator believes it is in the best interest of the patient. Novartis may be contacted by the investigator to discuss dosing options if the investigator so desires.

All dose modifications should be based on the worst preceding toxicity.	
a Core LFTs consist of ALT, AST, GGT, total bilirubin (fractionated [direct and indirect], if direct (conjugated) bilirubin > 2.0 x ULN), and alkaline phosphatase (fractionated [quantification of isoforms], if alkaline phosphatase > 2.0 x ULN.)	
b "Combined" defined as direct (conjugated) bilirubin increase to the defined threshold concurrently with ALT/AST increase to the defined threshold	
If combined elevations of AST or ALT and direct (conjugated) bilirubin do not meet the defined thresholds, please follow the instructions for isolated elevation of direct (conjugated) bilirubin and isolated elevation of AST/ALT, and take a conservative action based on the degree of the elevations (e.g. discontinue treatment at the situation when omit dose is needed for one parameter and discontinue treatment is required for another parameter). After all elevations resolve to the defined thresholds that allow treatment re-initiation, re-start the treatment either at the same dose or at one dose lower if meeting a criterion for dose reduction	

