### **6.2.4 Follow up on potential drug-induced liver injury (DILI) cases**

Patients with transaminase increase combined with TBIL increase may be indicative of potential DILI, and should be considered as clinically important events.

The threshold for potential DILI may depend on the patient's baseline AST/ALT and TBIL value; patients meeting any of the following criteria will require further follow-up as outlined below:

- For patients with normal ALT or AST or TBIL value at baseline: AST or ALT  $> 3.0 \times$  ULN combined with TBIL  $> 2.0 \times$  ULN
- For patients with elevated AST or ALT or TBIL value at baseline: [AST or ALT  $> 2 \times$  baseline AND  $> 3.0 \times$  ULN] OR [AST or ALT  $> 8.0 \times$  ULN], whichever is lower, combined with [TBIL  $> 2 \times$  baseline AND  $> 2.0 \times$  ULN]

Medical review needs to ensure that liver test elevations are not caused by cholestasis, defined as ALP elevation  $> 2.0 \times$  ULN with R value  $< 2$  in patients without bone metastasis, or elevation of ALP liver fraction in patients with bone metastasis.

Note: (The R value is calculated by dividing the ALT by the ALP, using multiples of the ULN for both values. It denotes the relative pattern of ALT and/or ALP elevation is due to cholestatic or hepatocellular liver injury).

In the absence of cholestasis, these patients should be immediately discontinued from study drug treatment, and repeat LFT testing as soon as possible, preferably within 48 hours from the awareness of the abnormal results. The evaluation should include laboratory tests, detailed history, physical assessment and the possibility of liver metastasis or new liver lesions, obstructions/compressions, etc.

- Laboratory tests should include ALT, AST, albumin, creatine kinase, total bilirubin, direct and indirect bilirubin, GGT, prothrombin time (PT)/INR and alkaline phosphatase.
- A detailed history, including relevant information, such as review of ethanol, concomitant medications, herbal remedies, supplement consumption, history of any pre-existing liver conditions or risk factors, should be collected.
- Further testing for acute hepatitis A, B, C or E infection and liver imaging (e.g. biliary tract) may be warranted.
- Obtain PK sample, as close as possible to last dose of study drug, if PK analysis is performed in the study.

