### 5.3.2 Laboratory data and vital signs

If two or more assessments are performed within a time window then the assessment closest to the planned visit is used in analyses by time window. When two values are equidistant from the planned assessment, the later one is used in analyses. When multiple values are reported on the same day then the average value is used in analyses. For parameters with categorical results, the one from central laboratory is used in analyses. If multiple values are reported on the same day from local and central laboratory, the central laboratory value is used in analyses. If only local lab assessments are collected, then local lab values are considered for analyses.

For worst post-baseline assessment, all on-treatment values are considered regardless of time windows.

[Table 5-4](#) shows the defined time windows.

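### The combined liver rows in the final SAP carry no same-sample or baseline condition, so they can exceed the cases that meet the protocol's potential-DILI criteria

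*SAP*

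**What the plan says.** **Final-CSR SAP, 2.7.4.2, Liver Function Parameters.** The basis for every row is: "The number (%) of subjects with worst post-baseline values as per Novartis Liver Toxicity guidelines will be summarized". Most rows are single-parameter thresholds. Three are combined: ALT or AST above 3xULN with TBL above 2xULN on its own, the same with ALP at or above 2xULN, and "ALT or AST > 3xULN & TBL > 2xULN & ALP < 2xULN". All limits are fixed multiples of ULN. No row mentions baseline, a common sample date or a time window.

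**Final-CSR SAP, 5.3.2.** "For worst post-baseline assessment, all on-treatment values are considered regardless of time windows".

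**Protocol, Table 6-2.** The block on combined elevations covers direct and/or total bilirubin. Its footnote b explains the word combined: "defined as direct (conjugated) bilirubin increase to the defined threshold concurrently with ALT/AST increase to the defined threshold". Where baseline is raised, the total-bilirubin entry reads: "AST or ALT>2x baseline AND >3.0xULN] OR [AST or ALT>8.0 ULN], whichever is lower, combined with total bilirubin >2x baseline AND >2.0xULN".

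**Protocol, 6.2.4.** "The threshold for potential DILI may depend on the patient's baseline AST/ALT and TBIL value". The second criterion opens "For patients with elevated AST or ALT or TBIL value at baseline" and applies the same baseline-relative limits. Cholestasis has to be ruled out, and is defined for patients without bone metastasis as ALP above 2xULN with an R value below 2.

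**Protocol, 5.3.** Direct bilirubin above 2xULN and ALT or AST above 3xULN exclude a patient. Total bilirubin has no limit. The Amendment 4 rationale remarks: "Many transfusion-dependent anemia patients have higher baseline level of direct bilirubin due to hemolysis".

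**The concern.** Hepatic toxicity is an actively monitored safety endpoint, and the combined rows are where a reader of the final report will look for a possible liver signal. For that use, the transaminase and bilirubin elevations should belong to one episode, and the bilirubin elevation should be new. The rows as written secure neither.

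Two features of this trial make the gap matter. Follow-up runs to week 305 with liver tests about every four weeks, so there are many chances for unrelated peaks. The patients have transfusion-dependent anaemias and may enter with raised total bilirubin through the indirect fraction, which no entry criterion limits.

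Any-time pairing also grows with time on treatment. The table sets patients randomised to granules (core plus extension) beside DT patients who crossed over (extension only). No comparison of these columns is planned, but they will be read side by side.

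**Working it through.** The plan gives no figure here to reproduce. The check compares the definitions, classifies test cases under each, and then illustrates the possible scale with assumed rates.

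**1. Test cases** (multiples of ULN)

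| Case | SAP row, read literally | Protocol 6.2.4 read with footnote b |
|---|---|---|
| A. Baseline ALT 1.0, TBL 2.5; later TBL 2.4 to 2.6; one ALT of 3.5 | Counted | Raised-baseline criterion: TBIL must exceed 2 x 2.5 = 5; not met |
| B. Normal baseline; ALT 3.5 at one visit, TBL 2.3 at a later visit | Counted | Not concurrent; not met |
| C. Normal baseline; ALT 3.5 and TBL 2.3 at one visit | Counted | Met, if not cholestatic |

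Case A needs a caveat. The first criterion in 6.2.4 is for patients with a normal ALT or AST or TBIL at baseline. Read literally, one normal value is enough, so case A (normal ALT) would also fall under the fixed ULN limits and be met at the visit with ALT 3.5. The text does not settle this. If ALT and AST are raised at baseline too, only the second criterion fits, and the 5xULN bilirubin limit keeps the patient out. Case B does not depend on this ambiguity.

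**2. The ALP split**

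- Worst ALP may come from another visit. It can only be equal to or higher than ALP on the date of the ALT and TBL elevation, so a case can be moved out of the row with ALP below 2xULN.
- The SAP split has no R value. With ALT 10xULN and ALP 2.5xULN, R = 10 / 2.5 = 4. That is not below 2, so it is not cholestasis under the protocol, yet the patient falls in the row with ALP at or above 2xULN.

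**3. Illustration of scale**

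Visits: clinical chemistry at core Visits 5 to 16 and 777 gives 12 + 1 = 13 post-baseline samples. Every 4 weeks from week 53 to week 305 gives (305 - 53)/4 + 1 = 64. The total is 77.

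Assumptions, none from the documents: the per-visit probability of ALT or AST above 3xULN is pA = 0.2% to 1%, that of TBL above 2xULN is pB = 2% to 10%, and they are independent of each other and across n visits.

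- Any-time pairing: (1 - (1 - pA)^n) x (1 - (1 - pB)^n)
- Same-visit pairing: 1 - (1 - pA x pB)^n

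| n | pA | pB | Any-time | Same visit | Ratio |
|---|---|---|---|---|---|
| 13 | 0.2% | 2% | 0.6% | 0.05% | 11.4 |
| 13 | 1% | 10% | 9.1% | 1.29% | 7.1 |
| 77 | 0.2% | 2% | 11.3% | 0.31% | 36.6 |
| 77 | 1% | 10% | 53.9% | 7.41% | 7.3 |

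Over the full grid the ratio is about 7 to 11 at 13 visits and 7 to 37 at 77.

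For the baseline route, assume 10% to 40% of patients have TBL above 2xULN at baseline and 10% to 20% have a later ALT or AST above 3xULN, independently. The overlap is 0.10 x 0.10 = 1% to 0.40 x 0.20 = 8%. This is an upper figure for excess by that route: some of these patients could also show bilirubin above twice baseline, and some would qualify under the literal reading of the first 6.2.4 criterion.

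**The case against.** The strongest reply is that the SAP does not say that values from different visits are to be paired. It defers to a sponsor liver guideline that is not in the documents and may set a timing rule, and section 5.3.2 says how the worst value of one parameter is found, not how two are joined. This stands as a limit: any-time pairing is the literal reading, not a stated rule.

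Four stronger readings are tempting, and the documents do not support them.

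- **That the protocol demands concurrent total-bilirubin elevations.** Footnote b is worded for direct bilirubin and sits in a dose-modification table. It hangs on a heading that covers total bilirubin as well, but 6.2.4 links ALT/AST and TBIL without any timing rule.
- **That the SAP departs from a planned analysis.** Protocol 10.5.4.2 and Table 10-1 plan no combined table. The rows are an addition.
- **That haemolysis would be counted as liver injury.** Raised bilirubin alone cannot fill a combined row, since ALT or AST above 3xULN is also needed. The SAP does not label the rows as DILI, and the amendment remark on haemolysis concerns direct bilirubin.
- **That the safety package cannot tell drug injury from disease.** Baseline-to-worst shift tables, changes from baseline, dated listings and a notable range for ALT/AST above 2x baseline are all planned. Confirmed cases with no other cause are reported as SAEs under 6.2.4.

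It is also fair that for patients with normal baseline the protocol's limits equal the SAP's, and that any-time rows are a legitimate sensitive screen. None of this supplies the missing pairing rule or a summary on the protocol's own criteria.

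**Conclusion.** The concern holds in a limited form. As written, the combined rows can pair ALT/AST, TBL and ALP values from different visits, and a stable raised baseline TBL satisfies the bilirubin part. The rows can therefore exceed the cases meeting the protocol's potential-DILI criteria, and the ALP split can misplace cases.

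The size cannot be determined. The ratios of 7 to 37 and the 1% to 8% rest wholly on assumed rates and independence; persistent or correlated elevations would change them. The conclusion needs only the literal reading of the two SAP sections, with case B as the example that depends on timing alone.

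The effect is on a descriptive table and how it is read. Dose decisions, follow-up and SAE reporting do not use it. This is a worthwhile and cheap improvement, not a flaw that undermines the safety analysis.

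**What to change.** In section 2.7.4.2:

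1. Keep the worst-value rows and label them as a sensitive any-time screen.
2. Add rows in which ALT or AST, TBL and ALP meet their limits on the same sample date, or within a short window stated in the SAP.
3. Add a row applying the protocol 6.2.4 criteria, with the baseline-relative limits and the cholestasis definition (ALP and R value). State how a patient with normal ALT/AST but raised baseline TBIL is classed. The protocol wording on this must be reconciled by the sponsor; no reading is proposed here.
4. List the patients counted in one set of rows and not the other.
5. If the sponsor's guideline already sets a pairing rule, write it into the SAP.

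The cost is SAP wording and a few table rows from scheduled laboratory data. The downside is smaller counts in the stricter rows, which is why the screen stays.
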